2.2 Secondary Objective (MCR site only)

Secondary objectives of this study are to evaluate, by proton magnetic resonance spectroscopy (¹H-MRS) at 3 Tesla (3T), the following neurometabolic biomarkers:

- 1) Define regional specificity [anterior cingulate (AC) and left dorsolateral prefrontal cortex (L-DLPFC)] of cerebral metabolites (i.e. glutamate and glutamine) in adolescent depression.
- 2) Study whether specific neurochemical resonances are associated with response or remission of clinical depressive symptoms when rTMS is used to treat adolescent depression.

To accomplish these goals, the MCR site will utilize ¹H-MRS, a valuable, non-invasive method to study in-vivo brain biochemistry. Of the available imaging paradigms, ¹H-MRS is uniquely suited to investigate biochemical mechanisms of treatment action that are objectively

measurable and clinically relevant. As there is increasing interest in glutamatergic dysregulation in mood disorders, this project will utilize ^1H -MRS at 3T to study specific neurometabolic levels in the primary brain regions associated with major depressive disorder [anterior cingulate (Brodmann's areas 24a/b and 32) and L-DLPFC (Brodmann's 9/46)]. The goal of this aspect of the proposal is to evaluate whether anterior cingulate and prefrontal cortex neurochemicals (such as glutamine), quantified as a cerebrospinal fluid (CSF)-corrected absolute concentration percent change from baseline, are associated with clinical remission of depression when active rTMS is used.

3 Study Design

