corpus callosum showing a continuous view of the anterior and posterior horns of the lateral ventricles will be chosen as a reference slice (Figure 2). The center of a single 4-cm³ voxel (2-x-2 cm in-plane resolution by 1 cm thick) of predominantly gray (prefrontal) matter is centered on the frontal interhemispheric fissure. The voxel's posterior margin is placed immediately anterior to the genu of the corpus callosum in an area corresponding to the pregenual AC cortex (Brodmann areas 24a, 24b, and 32). A second 8-cm³ voxel will be centered in white matter deep to the L-DLPFC, operationally defined as the gray matter of the superior frontal sulcus and large portions of the superior and middle frontal gyri, containing Brodmann's areas 9 and 46. A long echotime (TE=80 ms) standard PRESS sequence (TR=2000 ms, number of acquisitions=128, bandwidth 500 Hz, 4096 points) will be used to measure glutamate and glutamine as well as measure the other metabolites. A second 2D J-averaged MRS sequence (TE=35-195 ms in 16 steps of 10 ms each, TR=2000, number of acquisitions=128, bandwidth 500 Hz, 4096 points) will also be used to optimally measure glutamate in each voxel. All MRS data will be processed using LCModel, a well-accepted, unbiased program for determining metabolite concentrations. A quantitative analysis of brain metabolites will be performed with a focus on the target metabolites. Anatomical image data will be segmented into gray matter, white matter, and CSF using a semiautomated thresholding technique developed internally at MCR ([name], [name], [name]). This segmented anatomical data will be combined with the spectroscopic data to obtain tissue-volume-corrected metabolite concentrations per accepted methods. This generates "absolute" (versus relative to creatine) metabolite concentrations in "institutional units" specific to our scanner and technique. These concentrations will then be used in the statistical analysis. An accepted data standard for healthy controls in these particular voxel locations will be used in the comparison.

Figure 2 – Voxel Placement examples
Top = AC; Bottom = L-DLPFC

Phase II (Non-Randomized, Open-label):

Arm 1: Acute Treatment (Nonresponder Cohort)

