Treatment outcomes for both phases will be defined as response (CDRS-R raw score <28 & CGI-I ≤2 & CGI-S ≤2), or nonresponse (CDRS-R raw score ≥28 and CGI-I ≥3) assessed using a logistic regression model with independent variables of treatment number (i.e. #10 vs. #20 vs. #30) and gender (male vs. female) will be analyzed. Assessing potential gender effects will be a secondary analysis. The primary analysis will not adjust for gender. Although we anticipate that more females than males will participate in the study, we assume that the distribution of gender will be similar between treatment arms and have no a priori reason to suspect that the efficacy of treatment will be gender specific.

Serious adverse events will be reported as noted within the application. All adverse events will be summarized according to treatment groups. Given the sample size for the current study, the statistical power for detecting differences between groups is limited. However, we will compare between groups using an exact test.

All statistical tests will be performed at the 0.05 significance level.

Secondary Hypotheses (for MCR site only):

Baseline glutamate, reported as a CSF-corrected absolute concentration and as an overlapping resonance with glutamine, will be significantly higher in both AC and L-DLPFC in depressed adolescents as measured by ^1H -MRS at 3T when compared to data derived from previously scanned healthy controls.

In comparison to non-remission subjects, depressed adolescents treated with rTMS who achieve remission (defined as a CDRS-R raw score <28 and CGI-I ≤ 2 and CGI-S ≤ 2 at treatment completion) will exhibit a greater decrease in glutamine, reported as a CSF-corrected absolute concentration percent change (baseline to endpoint) in AC and L-DLPFC as measured by ^1H -MRS at 3T.

The hypotheses will be tested using t-tests. Additionally, analyses of covariance will be performed to control for potentially important covariates or confounders, such as age or gender. Non-parametric distribution will be analyzed by non-ANOVA statistics.

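### The MRS remission hypothesis does not state the arm or phase of its non-remitters, and baseline glutamine is not a named covariate

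*Combined protocol and SAP*

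**What the plan says.** The second secondary hypothesis in Section 7.2 (MCR site only) reads "In comparison to non-remission subjects, depressed adolescents treated with rTMS who achieve remission" and predicts a greater fall in glutamine in the remitters. The outcome is "reported as a CSF-corrected absolute concentration percent change (baseline to endpoint) in AC and L-DLPFC". On method, the section says "The hypotheses will be tested using t-tests" and adds that "analyses of covariance will be performed to control for potentially important covariates or confounders, such as age or gender".

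Section 2.2 states the aim more narrowly: whether neurochemical changes "are associated with clinical remission of depression when active rTMS is used".

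Section 3.1 (¹H-MRS methods) gives each MCR subject a baseline scan and a further scan at the end of each treatment phase. Sham subjects are not excepted. Under Section 6.3, nonresponders from either arm are offered 30 open-label active treatments in Phase II. Section 7.2 refers to treatment completion and endpoint without saying of which phase.

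**The concern.** In the Section 7.2 sentence, the words about rTMS treatment attach to the remitters only. An analyst following it literally would take active-arm remitters on one side and every scanned non-remitter on the other. Because sham subjects are expected to remit less often, most of that comparator would be sham. Remission and coil would then be confounded, and a direct effect of stimulation on glutamine would show up as a difference between remitters and non-remitters. The stake is a false remission biomarker from a small single-site sample.

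The phase gap adds to this. A subject randomized to sham who remits after Phase II active treatment has also been treated with rTMS, and an active non-remitter at the end of Phase I may be a remitter at the end of Phase II. The text does not say where either is counted.

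Separately, the main test uses percent change, and baseline concentration is not named as a covariate although it is measured in everyone who has a baseline scan.

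**Working it through.** **The plan's own figure.** No power is stated for the MRS hypotheses. The arm mix below rests on the success rates in Section 7.1, so those are checked first. With 65% against 25%, 35 per group and two-sided 0.05, the mean rate is 0.45:

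- (0.40 − 1.96·√(2·0.45·0.55/35)) / √((0.65·0.35 + 0.25·0.75)/35) = (0.40 − 0.233)/0.109 = 1.53, giving power 93.7% (stated 94%).
- With 25 per group the same formula gives 83.2% (stated 83%).

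**Inputs for the arm mix.**
- 50 subjects at MCR (Study Summary).
- 25 per arm at MCR. This is an assumption: Section 5.2 gives equal allocation overall but states no stratification by site.
- Remission rates of 65% active and 25% sham. This is also an assumption, taken from Section 7.1. Section 7.2 gives response and remission the same cutoffs, but those include a CGI-S limit that the Section 7.1 success rate does not mention.

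**Expected cells.**

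| | Active | Sham |
|---|---|---|
| Remitters | 25 × 0.65 = 16.25 | 25 × 0.25 = 6.25 |
| Non-remitters | 25 × 0.35 = 8.75 | 25 × 0.75 = 18.75 |

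Sham share of all non-remitters: 18.75/(8.75 + 18.75) = 18.75/27.5 = 68%. The share depends only on the rates, so equal attrition in both arms leaves it unchanged. With rates of 45%/25% it is 0.75/1.30 = 58%; with 65%/45% it is 0.55/0.90 = 61%.

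**Bias.** If the coil shifts glutamine change by d SD whatever the mood outcome, the literal contrast is off by 0.68·d: 0.20, 0.34 and 0.54 SD for d = 0.3, 0.5 and 0.8. The documents give no value for d, so these are assumed.

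**False-positive rate.** Simulation of 8,000 trials per setting, 25 per arm, normal outcome, no remission effect, nominal 5%:

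| Analysis | d = 0 | 0.3 | 0.5 | 0.8 |
|---|---|---|---|---|
| Active remitters vs all non-remitters | 5.3% | 10.1% | 19.0% | 37.4% |
| All remitters vs all non-remitters | 5.6% | 7.5% | 10.8% | 18.5% |
| Active remitters vs active non-remitters | 5.2% | 4.9% | 5.5% | 5.0% |
| All subjects, arm as covariate | 5.5% | 5.1% | 4.8% | 5.1% |

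**Power of the two sound options** for a true remission effect of 0.8 SD: about 45% for the active-only t-test (16 vs 9; detectable difference 1.22 SD at 80% power), and about 69% for the arm-adjusted model on all 50. Neither figure includes a gain from baseline adjustment.

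**Baseline adjustment.** With equal variance σ² at both scans and correlation r, raw change has variance 2(1 − r)σ² and ANCOVA has residual variance (1 − r²)σ². The ratio is (1 + r)/2: 0.65, 0.75 and 0.85 for assumed r of 0.3, 0.5 and 0.7. It applies to raw change and does not carry over exactly to percent change.

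**The case against.** The strongest reply is that Section 2.2 already limits the question to active rTMS. Read with it, the comparator in Section 7.2 is naturally the active-arm non-remitters; there is then no arm confounding and the 68% never arises. A reader might infer that the plan has committed to comparing with every non-remitter. It has not. What stands is that Section 7.2 never turns the Section 2.2 aim into an analysis population, and that an active-only reading would still leave the phase open.

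The second reply is that the covariate list is open. That is true: age and gender are examples, and Section 7.2 also tabulates baseline values of secondary outcomes to find covariates for sensitivity analyses, so baseline glutamine could be chosen. But the ANCOVA is additional to the t-tests, arm is not named, and a search for baseline imbalance between arms would not select arm itself.

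Third, any inflation needs a coil effect on glutamine. With none, the literal test keeps its nominal level.

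Some wider criticisms may be tempting, but the documents do not support them:
- *Tissue composition is ignored.* Section 3.1 segments the images "to obtain tissue-volume-corrected metabolite concentrations per accepted methods" and analyses those values.
- *The differing tissue in the two voxels biases the result.* Section 7.2 plans no test of one region against the other, and voxel placement is standardized.
- *The healthy controls come from another scanner.* Nothing in the documents shows this.
- *Four tests at 0.05 give 18.5% family error (1 − 0.95⁴).* This assumes four independent tests with every null true, and the glutamate hypothesis expects elevation in both regions.

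**Conclusion.** The point holds as an ambiguity with real consequences, not as proof that the plan uses a confounded comparison. Section 7.2 leaves the comparator's arm and phase unstated. Under the literal reading about 68% of the comparator is sham, and the false-positive rate rises to about 10%, 19% and 37% for arm effects of 0.3, 0.5 and 0.8 SD. Under the active-only reading it stays near 5%. These sizes rest on 25 per arm at MCR, on the Section 7.1 success rates standing in for remission rates, and on arm effects that the documents do not supply.

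The missing baseline covariate is a smaller matter of efficiency. The plan's open covariate list permits the adjustment but does not make it part of the main test.

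**What to change.** In Section 7.2:

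1. Define the analysis on the Phase I baseline and end-of-Phase-I scans, with remission judged at the end of Phase I.
2. For each region, make the main analysis an ANCOVA of end-of-Phase-I glutamine concentration on remission (yes/no), with baseline concentration and randomized arm as covariates, using all scanned Phase I subjects.
3. Report the active-arm contrast of remitters with non-remitters alongside, as the direct estimate for the Section 2.2 aim. State that it rests on about 16 against 9 subjects and has lower power.

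The cost is SAP text; the scans and ratings are already planned. The downside is that the arm-adjusted model assumes a similar association between remission and glutamine in both arms, with only about six sham remitters expected. The active-only estimate serves as a check on that assumption. Making the active-only contrast the sole analysis would avoid the assumption, but at 0.8 SD it would lower power from about 69% to about 45%.

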7.3 Subject Population(s) for Analysis

The primary analysis will use the intention-to-treat (ITT) population, defined as all patients who started at least one treatment session. Secondary analyses of the primary outcome will examine “completer” and “partially adherent” cohorts. The Completer Cohort will be defined as subjects treated according to the protocol with fewer than 10 rescheduled, missed, or partially completed rTMS sessions ultimately taking part in 30 treatment sessions. The Partially Adherent Cohort will have at least 20 completed or partially completed sessions without reaching the full 30-treatment threshold. Those with less than 20 completed or partially completed rTMS sessions will be analyzed within the intention-to-treat population.

8 Safety and Adverse Events

All Unanticipated Adverse Device Effects (UADEs) and severe, expected adverse events (AEs) at least probably related to the study treatment not meeting the criteria of UADE, including mania, exacerbation of depression, and suicidality will be recorded on the Adverse Event CRF and reported according to severity and the relationship of the AE to rTMS. Records of these events will be maintained and reports submitted to the FDA, regulatory sponsor, and reviewing IRBs according to local IRB policy and regulatory requirements. All other expected clinical adverse events and nonsignificant (not serious) clinical adverse events will be reported to all Principal Investigators on a periodic basis and reported to the appropriate IRB at the time of continuing review and to the FDA at the time of the Annual Report. Expected clinical adverse events and anticipated adverse device effects are those listed in Section 1.5.2.

8.1 Definitions

Unanticipated Adverse Device Effect (UADE)

A UADE is any serious adverse effect on health or safety or any life-threatening problem or death caused by, or associated with, a device if that effect, problems or death was not previously identified in nature, severity, or degree of incidence in the investigational plan or IDE application (including a supplementary plan or application), or any other unanticipated serious problem associated with a device that relates to the rights, safety, or welfare of subjects.

Adverse Effect (Event)

Any untoward medical occurrence in a subject involved in clinical study of an investigational device; regardless of the causal relationship of the problem with the device or, if applicable, other study related treatment(s).

Severity Ratings: **Mild (grade 1)** – a transient AE easily tolerated by the patient.

Moderate (grade 2) – an AE that causes the patient discomfort and interrupts the subject's usual activities, but does not interfere with function. **Severe (grade 3)** – an AE that causes considerable interference with the patient's usual activities.

Relationship to Treatment: **Definite** – AE is related. **Probable** – AE has a strong temporal relationship and another etiology is less likely. **Possible** – AE has a strong temporal relationship but an alternative etiology is likely. **Not Related** – AE is due to underlying or concurrent illness or drug effect.

General Physical Examination Findings

At screening, any clinically significant abnormality should be recorded as a preexisting condition. At the end of the study, any new clinically significant findings/abnormalities that meet the definition of an adverse event must also be recorded and documented as an adverse event.

Hospitalization, Prolonged Hospitalization or Surgery

Any adverse event related to the device that results in hospitalization or prolonged hospitalization should be documented and reported as an unanticipated adverse device effect unless specifically instructed otherwise in this protocol. Any condition responsible for surgery

should be documented as an adverse event if the condition meets the criteria for an adverse event.

Neither the condition, hospitalization, prolonged hospitalization, nor surgery are reported as an adverse event or UADE in the following circumstances:

- Hospitalization or prolonged hospitalization for diagnostic or elective surgical procedures for a preexisting condition. Surgery should **not** be reported as an outcome of an adverse event if the purpose of the surgery was elective or diagnostic and the outcome was uneventful.
- Hospitalization or prolonged hospitalization required to allow efficacy measurement for the study.
- Hospitalization or prolonged hospitalization for therapy of the target disease of the study, unless it is a worsening or increase in frequency of hospital admissions as judged by the clinical investigator.

Post-study Adverse Event

All unresolved adverse events should be followed by the investigator until the events are resolved, the subject is lost to follow-up, or the adverse event is otherwise explained. At the last scheduled visit, the local investigator should instruct each subject to report, to the local investigator, any subsequent event(s) that the subject, or the subject's personal physician, believes might reasonably be related to participation in this study. The local investigator should notify the study regulatory sponsor of any death or adverse event they become aware of that occurs at any time after a subject has discontinued or terminated study participation that may reasonably be related to this study. The regulatory sponsor should also be notified if the local investigator should become aware of the development of problems, cancer, or a congenital anomaly in a subsequently conceived offspring of a subject who has participated in this study.

Preexisting Condition

A preexisting condition is one that is present at the start of the study. A preexisting condition should be recorded as an adverse event if the frequency, intensity, or the character of the condition worsens during the study period.

Mayo Clinic-Specific Definitions

Unanticipated Problems Involving Risk to Subjects or Others (UPIRTSO)

Any unanticipated problem or adverse event that meets **all** of the following three criteria:

- **Serious:** Serious problems or events that result in significant harm, (which may be physical, psychological, financial, social, economic, or legal) or increased risk for the subject or others (including individuals who are not research subjects). These include: (1) death; (2) life threatening adverse experience; (3) hospitalization - inpatient, new, or prolonged; (4) disability/incapacity - persistent or significant; (5) birth defect/anomaly; (6) breach of confidentiality; and (7) other problems, events, or new information (i.e. publications, DSMB reports, interim findings, product labeling change) that in the opinion of the local investigator may adversely affect the rights, safety, or welfare of the subjects or others, or substantially compromise the research data, **AND**
- **Unanticipated:** (i.e. unexpected) Unanticipated problems or events are those that are not already described as potential risks in the protocol, consent/assent document, the Investigator's Brochure, or not part of an underlying disease. A problem or event is "unanticipated" when it was unforeseeable at the time of its occurrence. A problem or event is "unanticipated" when it occurs at an increased frequency or at an increased severity than expected, **AND**

- Related: A problem or event is "related" if it is possibly related to the research procedures.

MUSC-Specific Definitions

Unanticipated Problem Involving Risk to Subjects or Others (UPIRSO)

An Unanticipated Problem is an event refers to any incident, experience or outcome that:

1. is unexpected (in terms of nature, severity or frequency) given: (a) the research procedures described in the protocol-related documents , such as the IRB-approved research protocol and informed consent document; and (b) the characteristics of the subject population being studied;
2. is related or possibly related to a subject's participation in the research; and
3. suggests that the research places the research subjects or others at a greater risk of harm (including physical, psychological, economic, or social harm) related to the research than was previously known or recognized.

Adverse Event Reporting Period

For this study, the treatment follow-up period is defined as six months following the last administration of rTMS.

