There is a risk that the rTMS treatment may not be effective for some patients and that their depression may worsen. Concerns for theoretical mood destabilization, including induction of mania or worsening of suicidality, will be carefully considered throughout the course of treatment (at every treatment visit); and subjects, their families, and investigators may elect to discontinue the treatment protocol and withdraw from the study at any point. Furthermore, safety considerations consistent with current standard of care in child and adolescent psychiatric practice will be employed including contacting the primary mental health care provider, referral to on-call child and adolescent psychiatric services, referral to the emergency room, and/or hospitalization if necessary.

Several studies in the adult population and limited studies in the adolescent population have so far demonstrated the feasibility of rTMS to treat depression without any alarming indicators of exacerbation of depression or suicidality. [1, 7, 8, 11] However, pediatric use of antidepressant *pharmacotherapy* has corresponded with warnings about increases in suicidal ideation and behavior in youths and young adults treated with selective serotonin reuptake inhibitors (SSRIs). No compelling data are available to indicate whether the net result of treatment of depressed youths with these compounds is an overall increase or an overall decrease in the hazard of completed suicide; there is limited and inconclusive evidence in each direction.[13-17]

For the purposes of this study, exacerbation of depression will be defined as a CDRS-R score increase of >33% of baseline accompanied by clinician determination of significant clinical deterioration as noted by a clinical global improvement (CGI-I) scale score of ≥ 6 (much worse or very much worse). Exacerbation of suicidal ideation and behavior will be defined as an increase of the Columbia – Suicide Severity Rating Scale (C-SSRS) suicidal ideation score of ≥ 4 or suicidal behavior including actual suicide attempts, interrupted/aborted attempts, or preparatory acts or behavior.

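### Section 8.1 lets admissions for depression judged neither a worsening nor more frequent go unreported as adverse events, so psychiatric admissions can be under-counted in the by-arm safety comparison

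*Combined protocol and SAP*

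**What the plan says.** Section 8.1, under hospitalisation and surgery, first says that a device-related adverse event leading to admission is documented and reported as a UADE unless the protocol instructs otherwise. It then gives such instructions: "Neither the condition, hospitalization, prolonged hospitalization, nor surgery are reported as an adverse event or UADE in the following circumstances". The third circumstance is "Hospitalization or prolonged hospitalization for therapy of the target disease of the study, unless it is a worsening or increase in frequency". The frequency meant is that of admissions, and the investigator decides whether either exception applies. The lead-in removes the condition as well as the admission.

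Section 7.2 bases the safety comparison on adverse events: "All adverse events will be summarized according to treatment groups". It concedes low power: "Given the sample size for the current study, the statistical power for detecting differences between groups is limited". It still plans a formal comparison of the arms: "However, we will compare between groups using an exact test". No section lists psychiatric admissions by arm or makes them an endpoint.

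Other provisions bear on the point:

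- Section 8.1, preexisting condition: a condition present at the start is recorded as an adverse event if its frequency, intensity or character worsens.
- Section 1.4.2: exacerbation of depression means "a CDRS-R score increase of >33% of baseline accompanied by clinician determination of significant clinical deterioration", the latter shown by CGI-I of 6 or more. Suicidality has a separate C-SSRS and behaviour criterion.
- Section 4.4.1: for Phase II Arm 2, worsening is a CDRS-R rise above 33% or a raw score of at least 40, again with CGI-I of 6 or more.
- Sections 8 and 8.2: only UADEs and severe, expected events at least probably related to treatment go on the Adverse Event CRF. Other events stay in the source document or case history.
- Sections 8.5 and 8.6.1: the DSMB reviews serious adverse events monthly and other adverse events every six months.

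**The concern.** In this trial the target disease is the condition most likely to put a subject in hospital. Section 1.4.1 says that adolescents whose depressive symptoms persist are more likely to be admitted to psychiatric care. Persistence without deterioration is what the third exemption covers. The admission triggers that Section 1.4.2 adopts include social factors such as insufficient support at home, which need no change in a depression score.

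Whether such an admission is reported rests on one investigator's judgement of two undefined terms. The clause does not say what counts as a worsening. It does not say over what period, or against what history, an increase in frequency is assessed. Investigators at the two sites could handle the same admission differently and both follow the text.

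At stake is the completeness of a serious, easily verified outcome in the only randomised safety comparison the trial makes. An admission that is not an adverse event is not in the Section 7.2 table. It also cannot be a serious adverse event, so it has no stated route to the DSMB's monthly review.

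**Working it through.** **The text, followed through.** Take a Phase I subject whose depression has not improved and who is admitted for its treatment.

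1. Section 8.1, third exemption: the admission is for therapy of the target disease. Unless the investigator judges it a worsening or an increase in frequency, neither admission nor condition is reported.
2. Section 8.1, preexisting-condition rule: this restores the event only if the condition has worsened in frequency, intensity or character. Unchanged depression does not qualify.
3. Section 8.2: the case-history rule covers adverse effects. The admission may well be written down there, but nothing makes it a reported event.
4. Sections 8 and 8.2, CRF rule: even if the admission were classed as an adverse event, it would reach the Adverse Event CRF only as a UADE, or if severe, expected and at least probably related.
5. Section 7.2: the summary and exact test count adverse events. The admission is absent.

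**Size.** The plan states no admission rate and no power for safety comparisons, so there is no figure of its own to reproduce. The counts and rates below are assumptions. Group sizes are the planned 38 active and 37 sham (Study Summary), and the unit is a subject with at least one admission.

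*Sensitivity to one admission.* When all k admitted subjects are on sham, the table has probability C(37,k)/C(75,k).

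- k = 5: 435,897 / 17,259,390 = 0.0253. The mirror table, all five on active, has probability 501,942 / 17,259,390 = 0.0291. This is larger, so it does not enter the two-sided p-value. Fisher p = 0.025.
- k = 4: 66,045 / 1,215,450 = 0.0543. The mirror table has 73,815 / 1,215,450 = 0.0607 and again does not enter. Fisher p = 0.054.

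Five against none is the smallest excess on sham that reaches 0.05. In the other direction it is six on active against none on sham (p = 0.025), and dropping one gives p = 0.054.

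*Equal loss in both arms.* Let the true admission rates be pA (active) and pS (sham), and let a fraction c be reported in each arm. Power is the sum, over all tables with two-sided Fisher p ≤ 0.05, of Bin(a; 38, c·pA) × Bin(b; 37, c·pS).

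| Assumed rates, active vs sham | c = 1 | c = 0.75 | c = 0.5 |
|---|---|---|---|
| 5% vs 15% | 24% | 15% | 6% |
| 5% vs 20% | 48% | 32% | 15% |
| 5% vs 25% | 69% | 51% | 27% |

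For the middle row, full reporting gives expected counts of 0.05 × 38 = 1.9 and 0.20 × 37 = 7.4. Half reporting gives 0.95 and 3.7. The ratio is unchanged, but little is left to test.

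**The case against.** The strongest reply is that the gap is narrow. The exemption has two exceptions, not one. A subject who was not being admitted before the trial and is admitted during it can be called an increase in frequency, and the preexisting-condition rule covers any rise in intensity with no numerical threshold. Sections 8 and 1.4.2 also name exacerbation of depression and suicidality as events to record. Read generously, these bring many admissions back. That stands, and it limits the point to admissions judged neither a worsening nor more frequent. It does not remove the point, because the clause leaves that judgement without a criterion.

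Several stronger readings are tempting, but the documents do not support them.

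- *The loss biases the active-sham comparison.* Section 5.7 blinds treating and assessing staff in Phase I, so nothing shows that classification would differ by arm. Phase II judgements are open-label, but Phase II is uncontrolled and, by Section 7.2, exploratory and mainly descriptive.
- *An admission counts only after a CDRS-R rise above 33%.* The exemption cites no cutoff. The 1.4.2 definition is not the only one in the protocol, and none is tied to this clause.
- *Section 8.1 contradicts itself by calling every admission serious.* The phrase "hospitalization - inpatient, new, or prolonged" belongs to one of three joint criteria in the Mayo Clinic definition of an unanticipated problem for IRB reporting. It is not a general rule. The UADE rule for device-related admissions expressly gives way to other instructions in the protocol.
- *The primary safety endpoint is undermined.* Section 3.4 counts treatment-related UADEs. An admission for lack of improvement would rarely enter that endpoint with or without the exemption.
- *The admissions vanish from all records.* They may remain in the case history. They are lost from reporting and analysis.

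**Conclusion.** The gap is real and limited in size. As written, Section 8.1 allows an admission for persistent depression to go unreported as an adverse event on an unguided judgement. Section 7.2 then has no means of counting it, and the DSMB has no stated means of seeing it. The consequence to expect is under-counting and lost power in a comparison the plan already describes as weak.

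The numbers are illustrations. They rest on the planned 38 and 37 subjects, on assumed admission counts and rates, and, in the power table, on reporting that is equally incomplete in both arms. Within that range, one unreported admission can move a result across 0.05, and reporting half of the admissions cuts power from 24–69% to 6–27%. How many admissions would be affected cannot be known from the documents. This is a cheap improvement to recording and analysis and does not call the design into question.

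**What to change.** 1. In Section 8.1, remove the third exemption or narrow it to admissions already scheduled before consent.
2. Record every psychiatric admission after randomisation on a CRF, with date and reason, and with relatedness recorded separately, whatever its adverse event classification.
3. Amend the rule in Sections 8 and 8.2 that limits the Adverse Event CRF to UADEs and to severe, expected events at least probably related to treatment, so that these admissions pass through. Changing 8.1 alone would leave this filter in place.
4. In Section 7.2, tabulate all psychiatric admissions by randomised arm for Phase I, and descriptively by arm for Phase II.
5. Reconcile the 8.1 exemption with the worsening definitions in 1.4.2 and 4.4.1 and with the preexisting-condition rule. This review takes no view on which clinical threshold is right.

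The cost is text changes in four places (8.1, the opening of 8, 8.2 and 7.2), the reconciliation in item 5, a few more event forms and one more table. No visits or assessments are added.
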